5.5.3 Vaccination

Enrollment visit

- Participants who elect to get the 2023-2024 updated COVID-19 vaccine will be able to self-schedule a future vaccination visit immediately after they have given consent. Study staff will confirm their appointment approximately 7-14 days before the start of study vaccine administration if participants are enrolled before study vaccine is available on site. Participants will be able to re-schedule or cancel appointments using the self-scheduling application. Participants may "walk-in" to vaccination sites and complete pre-vaccination activities on the same day as vaccination. At the vaccination visit, study staff will complete a brief questionnaire to determine if a COVID-19 vaccine can be given (Appendix K. Pre-Vaccination Questionnaire) to the participant. If it is determined that administration of the COVID-19 vaccine may need to be delayed a follow-up appointment will be made. Participants will have the option at this visit of changing their minds and participating in the non-vaccinated arm of the study if they wish and if there is still space available.
- Participants who decline to get the 2023-2024 updated COVID-19 vaccine but consent to take
 part in the study will also come in for the enrollment visit. These participants will be able to selfschedule their Study Visit immediately after they have given consent. Study staff will confirm
 their appointment approximately 7-14 days before their enrollment visit. Participants will be
 able to re-schedule or cancel appointments using the self-scheduling application. Participants

may "walk-in" to vaccination sites and enroll in the study even if they decline to get the vaccine. At the enrollment visit, study staff will distribute weekly and illness surveillance kits and provide instruction. Participants will have the option at this visit of changing their minds and participating in the vaccinated arm of the study if they wish and if there is still space available.

Randomization

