6.1 Sample size & Power Considerations

6.1.1 Sample Size for Primary Objectives

Power and sample size are examined for both primary objectives to 1) compare VE between vaccinated arms (both NVX and mRNA) and the non-vaccinated comparison arm with a 2-sided alpha=0.05 superiority test and 2) determine non-inferiority of NVX 2023-2024 formula vaccine variant compared to a single dose of Pfizer mRNA 2023-2024 updated vaccine with a 1-sided alpha=0.05 confidence interval. The rate of CLI-associated SARS-CoV-2 infection, confirmed by COVID-19 rapid antigen test (RAT) in those not vaccinated with the 2023-2024 formulation is expected to be 60 per 100,000 person-days. We expect those choosing not to vaccinate in Fall 2023 to Spring 2024 to be a mix of unvaccinated and fully vaccinated but not boosted individuals, but to be conservative we will assume this group is solely comprised of fully vaccinated individuals. Using publicly available data on the historic case rates in Utah for COVID-19 from the week of November 20, 2022 to the week of July 30, 2023, 39 the average rate of cases in those fully vaccinated in Fall 2022-Spring 2023 is 39.64 per 100,000 person-days for those fully

vaccinated. From a survey conducted in spring of 2022, it has previously been reported that of those testing for COVID-19 44.2% report testing at a lab or clinic and 25.7% reported testing at a drive-thru clinic⁴⁰. Therefore, using at-home test kits to identify cases, we expect rates to be 43.1% higher (1/(0.257+0.442)) than what is shown on Utah's dashboard. This under-reporting adjustment to Utah's observed rates from last fall leads to a conservative estimate for the rate of CLI-associated SARS-CoV-2 infection, confirmed by COVID-19 rapid antigen test (RAT), in those not vaccinated with the 2023-2024 formulation to be 60 per 100,000 person-days. Using the same logic applied to the reports for those with a bivalent booster last fall, after adjusting for under-reporting, we estimate the infection rate to be 48 per 100,000 person-days in those vaccinated in Fall 2023 to Spring 2024.

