For the superiority test of the first primary objective, on which the sample size is based, the null hypothesis that vaccine efficacy, or VE, of the 2023-2024 formula compared to no vaccination in Fall 2023-Spring 2024 is 0 is tested against the alternative that the VE is not equal to 0. That is, H_0 : VE = 0 is tested against H_a: VE ≠ 0. VE is calculated as 1- hazard ratio, HR, comparing those receiving the 2023-2024 formulation (either NVX or Pfizer) to those choosing not to be vaccinated in Fall 23 to Spring 24, times 100 or 100*(1-HR). HR will be estimated using Cox proportional hazards models with α =0.05. Table 4 provides the required sample size to yield 80% power to detect VE of 40%, 50%, and 60% or higher, assuming an attrition rate of 15% or less. We plan that the NVX and Pfizer arms will each have twice as many participants as the arm of those choosing no Fall 2023 to Spring 2024 vaccination, a ratio of 4:1. Calculations were made in PASS using the Multi-Arm Tests for Treatment and Control Survival Curves using Cox's Proportional Hazards Model⁴¹. In 24 weeks of follow-up, the rate of 60 cases per 100,000 person-days equates to an event probability of 10.08%. This probability corresponds to a hazard rate of 0.10625. With a total of 1500 participants enrolled (1200 with 2023-2024 formulation and 300 without Fall 2023 to Spring 2024 vaccination), we have 80% power to detect a VE of 56.25% or more, even if we see 15% attrition. With 1500 enrolled and an observed VE of 50%, we anticipate there will be approximately 85 RAT confirmed symptomatic COVID-19 cases in total (30 in the not vaccinated arm and 55 in the vaccinated arm) with no attrition, and 72 with 15% attrition.

Table 4. Relationship between Vaccine Efficacy and Sample Size, assuming a 4:1 ratio vaccinated						
with 2023-2024 formulation to not vaccinated in Fall 2023-Spring 2024 and 15% rate of attrition.						
Lowest Detectable VE comparing between non-vaccinated and Sample size for 80% power						
vaccinated (NVX and Pfizer combined) arms						
40%	3,183					
50%	1,954					
56.25%	1,500					
60%	1,289					

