# 1.2 Study Endpoints

# 1.2.1 Primary Endpoint

Time from enrollment in the study or start of active surveillance, whichever is later, to CLI-associated SARS-CoV-2 infection, confirmed by COVID-19 rapid antigen test (RAT).

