#### 6. ANALYSIS POPULATIONS

#### **6.1 Modified Intent-to-Treat Population**

All participants who are randomized, received a study vaccine, and participated in study surveillance by responding to at least one surveillance contact during the SARS-CoV-2 circulation period (active surveillance) will be included in the modified intent-to-treat (mITT) population for the primary objectives. The mITT population will be the primary population for efficacy analyses and participants are analyzed according to their randomized treatment. For participants who were identified as not receiving a booster

(comparison group) they will be analyzed in that group under the mITT population, even if they subsequently do get a vaccine during the study period.

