# **Efficacy**

#### Time at Risk

- Beginning of time at risk starts with the first active surveillance contact
- End of time at risk is illness onset with rapid test confirmed SARS-Co-v2 virus infection or the last submitted response to study surveillance.
  - o Illness onset is defined for participants with an illness as the earlier of the first positive swab collection (excluding false positives) and the date of reported symptom start.
- Duration of time at risk in days is defined as: End of time at risk beginning of time at risk + 1.
- We will assess the need to statistically adjust for time since last infection or time since last vaccination as 2 separate potential covariates

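### Time at risk is not tied to the study dose, so for vaccinees whose dose is deferred, largely event-free pre-dose days can be counted as vaccinated time and push VE upward

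*Protocol*

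**What the plan says.** **Deferral of the dose.** Protocol 5.5.3 has staff complete a questionnaire at the visit to decide whether the vaccine can be given, and adds: "If it is determined that administration of the COVID-19 vaccine may need to be delayed a follow-up appointment will be made". The same paragraph has staff confirm appointments ahead of the start of vaccine administration "if participants are enrolled before study vaccine is available on site".

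**Start of surveillance.** The protocol's opening summary, 5.2 (Study Duration) and 5.5.2 all start active surveillance for participants directly after the enrollment visit. None of them makes an exception for an intended vaccinee not yet dosed.

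**Start of time at risk.** SAP 1.2.1 defines the endpoint as "Time from enrollment in the study or start of active surveillance, whichever is later", up to the confirmed illness. SAP 7.5 says: "Beginning of time at risk starts with the first active surveillance contact". Neither refers to the dose. Protocol 6.1.2 gives no start date.

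**Who is analyzed.** For the vaccine arms, SAP 6.1 admits to the mITT population "All participants who are randomized, received a study vaccine, and participated in study surveillance by responding to at least one surveillance contact". Protocol 5.3 excludes anyone with a confirmed infection in the 90 days up to trial vaccination. Protocol 5.1 and 5.5.3 place randomization at the vaccination appointment, once a same-day dose has been confirmed as possible.

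**The concern.** The first primary comparison, vaccinated against decliners, is not randomized, so nothing in the design offsets a difference in how the two groups' clocks start. If a vaccinee's clock starts before the dose, the early days are guaranteed to be nearly event-free. Someone infected in the gap is normally not dosed, hence not randomized and not in the mITT vaccine arms, while someone who stays well is dosed later and brings those well days along. A decliner's infection counts from the start of that person's time at risk. This is immortal time in one group only. It lowers that group's hazard even if the vaccines do nothing.

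A few points could matter. The infection rates in protocol 6.1.1, 48 per 100,000 person-days vaccinated and 60 unvaccinated, imply a VE of only 1 - 48/60 = 20%.

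**Working it through.** **1. Does the plan permit pre-dose time at risk?**

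- *Planned path.* The Schedule of Activities puts the pre-vaccination questionnaire, randomization, vaccination and kit distribution on Day 0. Protocol 5.5.1.2 gives the vaccine at the enrollment visit, 5.6.1 hands out kits at the vaccination visit, and Table 7 starts surveillance on Day 0, which is also the vaccination day. Protocol 5.2 treats enrollment and vaccination as one date for the 24-week clock. Time at risk then starts on or after the dose, and the problem does not arise.
- *Deferred path.* The person attends the visit, the dose is put off, and surveillance starts after that visit under 5.2 and 5.5.2. Both SAP start dates can then precede the dose. Taking the later of two dates does not help when both come before it. No text says that surveillance waits.

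**2. The plan's own figure.** Inputs from protocol 6.1.1: the test is planned "with a 2-sided alpha=0.05 superiority test"; "the rate of 60 cases per 100,000 person-days equates to an event probability of 10.08" percent over 24 weeks (168 days); allocation is 4:1.

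- Event probability: 60/100,000 × 168 = 0.1008. Hazard: -ln(1 - 0.1008) = 0.10625, as stated.
- Events needed at VE 56.25% (HR 0.4375): (1.960 + 0.842)² / [0.2 × 0.8 × (ln 0.4375)²] = 71.8, so 72.
- Mean event probability: 0.2 × 0.1008 + 0.8 × [1 - exp(-0.10625 × 0.4375)] = 0.0565.
- N = 71.8 / 0.0565 / 0.85, about 1,495 before rounding of inputs.

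This agrees with the stated 1,500 and with the claim that "we have 80% power to detect a VE of 56.25% or more, even if we see 15% attrition". The calculation makes no allowance for pre-dose time, so it describes the planned path.

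**3. Size of the bias.** Let a share f of vaccinees have d event-free pre-dose days counted. At a constant hazard their events fall only in the remaining time, so

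- apparent HR ≈ (1 - VE) × (1 - f·d/168)
- bias in VE ≈ (1 - VE) × f·d/168

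To first order the infection rate cancels. The table sets this beside a large-sample solution of the Cox score equation on daily risk sets, with a control hazard of 60 per 100,000 per day. All values of f and d are assumptions.

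| f | d (days) | f·d/168, in points | Cox bias, true VE 0 | Cox bias, true VE 20% | Cox bias, true VE 50% |
|---|---|---|---|---|---|
| any | 0 | 0 | 0 | 0 | 0 |
| 5% | 14 | 0.42 | 0.44 | 0.34 | 0.21 |
| 10% | 14 | 0.83 | 0.88 | 0.69 | 0.43 |
| 25% | 28 | 4.17 | 4.37 | 3.48 | 2.16 |
| 100% | 14 | 8.33 | 8.72 | 6.95 | 4.32 |

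The Cox values are slightly larger because somewhat more events fall early, while more people remain at risk. With time zero at the dose, the same model returns the true VE in every row, to within 0.01 point.

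**4. Effect on the test at true VE 0.** Take f = 25%, d = 28, with 15% attrition. Expected events are 0.85 × [300 × 0.1008 + 1200 × 0.1008 × (1 - 7/168)] = 124.2. The shift in the test statistic is √(124.2 × 0.16) × |ln(1 - 0.0437)| = 0.199. Two-sided rejection is Φ(0.199 - 1.96) + Φ(-0.199 - 1.96) = 0.055. The same steps give 0.050 for 10% deferred by 14 days and 0.069 for a 14-day gap in all vaccinees.

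**5. The relative comparison.** Deferral happens before randomization, so it should be balanced between NVX and Pfizer. The rVE is left essentially unbiased.

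**The case against.** The strongest reply is that the documents describe a design with no pre-dose follow-up, as step 1 shows. That stands for everyone dosed at the enrollment visit.

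It is also fair to say that the reference to enrollment before vaccine is on site is weak evidence of a gap. In 5.5.3 those people have consented and booked a future vaccination visit; they have not clearly attended the visit that supplies kits and starts surveillance. The Schedule of Activities does mark weekly screening questions in the screening column, but not for vaccinees specifically, and kits appear only at Day 0. The sentence in 5.5.1.2 giving kits to all participants whether or not vaccinated may simply contrast acceptors with decliners. The point therefore rests on the deferral sentence together with the start-of-surveillance text.

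Nor are the pre-dose days strictly event-free. That is an inference from the 90-day exclusion and the mITT definition, not a stated rule. Someone dosed more than 90 days after an infection in the gap could have that infection scored as a vaccine failure, which pulls the other way. With dosing planned for November through February, there is limited room for this.

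What the reply does not remove is the omission. The protocol lets the enrollment visit and the dose fall on different days, and the SAP does not say which one governs.

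**Conclusion.** The point holds as a gap on an exception path. For deferred vaccinees the plan as written can count pre-dose days as vaccinated time, and the net bias in VE against decliners is upward. Its size depends on two quantities that the documents do not give. For few and short deferrals it is under 1 point and the test's level is practically unchanged. It becomes material only if deferrals are common or long, for example 4.4 points at true VE 0 with a quarter deferred by four weeks. It shrinks in proportion to 1 - VE. These figures assume a constant hazard and no countable event before the dose.

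A reader might infer that pre-dose days are credited to the vaccine arms as a matter of course, with a bias near 9 points. The documents do not support this. That figure needs a two-week gap for all vaccinees, contrary to the Day 0 schedule. A reader might also infer that the non-inferiority result is compromised; because deferral precedes randomization, it is not.

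**What to change.** In SAP 1.2.1 and 7.5, and in protocol 6.1.2, state one rule:

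- Time at risk starts, for vaccinated participants, at the later of the study dose date (Vaccine Administration Form, Appendix L) and the first active surveillance contact.
- For decliners it starts at the later of the enrollment visit and the first active surveillance contact.
- No contact, test or illness before that date counts as time at risk or as an event.

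Report the distribution of days from enrollment to dose, so that readers can see how often the two dates differed.

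Using the later of the two dates keeps the SAP's present start at first contact and adds only the dose condition. The cost is one sentence per location and one descriptive summary. The dose date is already recorded, the person-days lost are few, and on the planned path nothing changes.

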5.5.3.1 Immunization Information Systems

Study staff will query the state immunization information system (IIS) or registry to obtain COVID-19, and influenza vaccination status or history. Participants will be asked to consent to this data collection in the consent form and may opt out of having their vaccine records obtained by the study. Administration of COVID-19 vaccines may need to be documented by public health jurisdictions within 24 hours of administration. Study staff will work with IIS personnel to determine the appropriate procedures to document COVID-19 vaccination receipt. The process for collection of vaccine record data will be outlined in Appendix N1: Vaccine Abstraction Verification and Appendix N2: Vaccine Abstraction Verification End-of-Year.

5.5.3.2 Vaccination Reporting

Influenza vaccination status will be reported by the participants (including type of vaccine, location, and date of vaccination) through the Mid-Study and End-of-Study (Appendix O) Surveys. Receipt of 2023-2024 updated COVID-19 vaccine outside of the study during the study period will similarly be self-reported through the Mid-Study and End-of-Study Surveys. Should a participant in the non-vaccinated arm of the study receive an updated COVID-19 vaccine during the study period, that information will be captured via the Mid-Study Survey & End-of-Study Surveys (Appendix O), or the Vaccine Abstraction Verifications (Appendix N1-N2) but the participant will remain in the study. Participants will also be asked to provide their COVID-19 and influenza vaccination history through self-report and the upload of vaccine documentation to their participant dashboard. Examples of documentation include a digital photo of the vaccination receipt or immunization records. These documents can be uploaded only via the participant dashboard.

In addition to the responses provided in the eligibility and enrollment surveys, previous COVID-19 vaccination data will be retrieved through USIIS by study staff or provided by the participant (vaccine card or immunization records) to determine eligibility. The study team will collect the vaccine manufacturer information. This information is important due to the exclusion criteria centered around receipt of the J&J vaccine. There were a small proportion of Utah residents who received the J&J Vaccine (<8%, 166581/2082443). The vaccine type, other than J&J, will represent what is commonly done in pragmatic study designs. The study team will track the prior vaccination manufacturer to see if there may be interactions between different combinations of vaccines. From a clinical perspective there is no concern with a heterologous vaccination approach, as there have been a number of studies which demonstrate that such an approach is clinically appropriate. This has led to the CDC issuing guidance supporting "mix-and-match" vaccine strategy.

5.5.4 Follow-up Surveys

Brief surveys will be administered over the course of the study for three purposes. First, surveys will allow participants to update information on their occupation and work responsibilities, health status, potential exposures to COVID-19 at work, home, and in the community, and their use of PPE in these settings. Second, surveys will allow participants to report if they were unable to report a qualifying illness and/or submit illness specimens for any reason, and to provide an estimate of when this missed illness event occurred so that their surveillance record can be updated accordingly. Third, surveys will assess participants KAP regarding COVID-19 vaccines, intention to be vaccinated, and then after vaccination, to recall their overall health status on the days following vaccination.

- Post-Vaccination Survey (Appendix W. Post-Vaccination Survey), for participants who choose to receive a COVID-19 2023-2024 updated vaccine, will be administered 24 hours ±1 day, 48 hours ±1 day, and 6 days ±1 day after receiving the vaccine in order to monitor events for 168 hours following vaccination.
- Follow-up Survey 1 (Appendix O. Mid-Study Survey) will allow participants to report any adverse
 events following immunization (AEFI), and update chronic medical conditions, KAP responses,
 occupational, exposures, PPE use, and employer-mandated COVID-19 vaccination requirements.
 This survey will also give participants an opportunity to report their influenza vaccination status
 for the season. Participants also can report any illnesses missed during surveillance. All

- participants will be asked supplemental questions to collect information about receipt of COVID-19 vaccines outside of the study during the study period.
- Follow-up Survey 2 (Appendix O. End-of-Study Survey) will provide a final opportunity to allow participants to report any AEFI, and update chronic medical conditions, KAP responses, occupational, exposures, PPE use, and employer-mandated COVID-19 vaccination requirements. This survey will also give participants an opportunity to report their influenza vaccination status for the season. Participants also can report any illnesses missed during surveillance. All participants will be asked supplemental questions to collect information about receipt of COVID-19 vaccines outside of the study during the study period.
 - o If participants indicate they want to withdraw from the study before completing the follow-up period, they will be invited to complete the End-of-Study Survey before withdrawal. Specific efforts will be made to collect survey responses from participants who did not complete the full follow-up period. The protocol status of all participants will be tracked in the database platform to record early termination, loss to follow-up, participant-directed withdrawal, and protocol completion. Utah study staff will complete the Participant Withdrawal Form (Appendix R5) for each participant who chooses to withdraw from the study.
- Long COVID Survey (Appendix P) will provide participants an opportunity to report Long COVID symptoms that last longer than 1 month. The survey will be distributed to participants with a first positive COVID-19 rapid test within the study (cases) and also participants who report their first COVID-like illness (CLI) symptoms during the study but did not test positive on the rapid test (controls). The survey will ask participants to identify which symptoms lasted more than 1 month, duration of these symptoms, and how these symptoms impact function and mental health. The Long COVID Survey will be distributed at the same time as the Mid-Study and End-of-Study Surveys.

Table 3. Survey Instruments and Timing

Instrument	Instrument Appendix Title Purpose		Purpose	Timing
Post- Vaccination Survey	W	Post- Vaccination Survey	To monitor for adverse events by answering questions about reactions to the vaccine for participants who choose to receive the COVID-19 2023-2024 updated vaccine	Day 1, Day 2, and Day 7 post- vaccination
Follow-up Survey 1	0	Mid-Study Survey	Self-reported documentation AEFI; update chronic medical conditions, KAP responses, occupational, exposures, PPE use, and employer-mandated COVID-19 vaccination requirements; report any illnesses missed during surveillance. They will be asked supplemental questions to collect information about receipt of COVID-	December 2023/January 2024

			19 vaccines outsides of the study during the study period.	
Follow-up Survey 2	0	End-of-Study Survey	Same as Mid-Study survey	April/May 2024
Long COVID Survey	Р	Long COVID Survey	The intended recipients are participants who had an illness that lasted longer than 4 weeks. The survey asks about symptoms that lasted at least 4 weeks, how long each symptom lasted, and how bothersome the symptoms were. The survey also asks questions about mental health of the participant.	Distributed to all cases and controls at the same time as the Mid-Study and End-of- Study surveys.

